##### 4.10.1.2. AESI

AESI definition are based on MedDRA Coding version 17.1.

An overall summary of AESI and DLT will be presented. AESI will be summarized by SOC and PT and for AESI4, a summary of liver function test elevation will be presented. AESI will be reported in listings.

###### 4.10.1.2.1. AESI1: Atelectasis

Atelectasis is defined as the AEs of at least Grade 2 with the preferred term that contains "atelectasis".

#### 4.10.1.2.2. AESI2: Hypotension

Hypotension is defined as the AEs of at least Grade 2 with the preferred term that contains any of terms below:

- Blood pressure ambulatory decreased
- Blood pressure decreased
- Blood pressure diastolic decreased
- Blood pressure orthostatic decreased
- Blood pressure systolic decreased
- Diastolic hypotension
- Hypotension
- Mean arterial pressure decreased
- Orthostatic hypotension
- Procedural hypotension

#### 4.10.1.2.3. AESI3: Bronchospasm

Bronchospasm is defined as the AEs of at least Grade 2 with the preferred term that contains "Bronchospasm" or "asthma" or "wheezing" or "bronchial obstruction"

#### 4.10.1.2.4. AESI4: Liver Function Test Elevation

Liver Function Test Elevation is defined from laboratory data as: Alanine Aminotransferase (ALT) >3 x ULN or Aspartate Aminotransferase (AST) >3 x ULN and doubling from baseline value.

#### 4.10.1.2.5. AESI5: Pneumonitis

Pneumonitis is defined as the AEs of at least Grade 2 with the preferred term that contains "pneumonitis".

#### 4.10.1.2.6. AESI6: Crackles

Crackles is defined as the AEs of at least Grade 2 with the preferred term that contains "crepitation" or "rales".

#### 4.10.1.2.7. AESI7: Dypnoea

Dyspnoea is defined as the AEs of at least Grade 2 with the preferred term that contains "dyspnoea" or "orthopnoea".

#### 4.10.1.2.8. AESI8: Hypoxia

Hypoxia is defined as: Pulse Oximeter < 88%

#### 4.10.1.2.9. AESI9: Allergic Reaction

Allergic Reaction is defined as the AEs of at least Grade 2 with the preferred term that contains "Hypersensitivity" or "Alveolitis" or "vasculitis" or "urticaria" or "dermatitis allergic" or "anaphylactic" or "anaphylaxis".

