5.5 Study Completion and Discontinuation Criteria

5.5.1 Study Completion/Withdrawal

A subject will have the right to withdraw from the study at any time for any reason.

A subject will be discontinued from the study by the Investigator if unacceptable toxicity or withdrawal of consent occurs.

Subjects participating in a MAD cohort that is determined to be greater than the MTD based on dose escalation rules can opt to continue in the study at the next lower dose cohort (ie, at the MTD).

Subjects withdrawn from SAD cohorts should have all assessments conducted at the End of Study Visit at the time of withdrawal. Subjects withdrawn from MAD cohorts should have all

assessments conducted at the End of Treatment Visit as well as the End of Study Visit, for safety monitoring purposes.

Subjects who have completed a SAD cohort are eligible to participate in a MAD cohort, provided there is at least 90 days between the dose in the SAD cohort and the first dose in the MAD cohort.

Allergic reactions may include local dermatitis, angioedema, throat constriction, or anaphylaxis. Appropriate treatment may include administration of antihistamines, hydrocortisone, or epinephrine at the discretion of the assessing physician. Subjects diagnosed with a systemic allergic reaction requiring therapy will be withdrawn from the study.

Given the proposed mechanism of action of QR-010, it could be anticipated that subjects could experience a change in baseline cough, change in sputum quality, or change in sputum volume. A pulmonary exacerbation should be considered if these symptoms are accompanied by fever, body weight loss, generalized malaise. If a pulmonary exacerbation is diagnosed, appropriate interventions including appropriate additional antibiotics should be prescribed by the Investigator or treating physician. Subjects diagnosed with a pulmonary exacerbation requiring the addition of antibiotics will be withdrawn from the study.

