12.4.3 Recording Adverse and Serious Adverse Events

Investigators should use correct medical terminology/concepts when recording AEs or SAEs on the CRF and/or SAE form. Colloquialisms and abbreviations should be avoided. SAEs must also

be recorded on the AE CRF. Only one medical concept should be recorded in the event field on the AE CRF and SAE form (if applicable).

a. Signs and Symptoms versus Diagnosis

Signs and symptoms should be recorded on the AE CRF rather than the unifying diagnosis. The unifying event term or diagnosis should be recorded as the “etiology” in the CRF (if known), and the SAE form, if applicable. For example, jaundice, asterixis, and elevated transaminases should be recorded on the CRF, and “liver failure” should be recorded as the etiology. As another example, cough, rhinitis, and sneezing should be recorded as AEs on the CRF, and record “upper respiratory tract infection” as the etiology. Vague, nonspecific AE terms such as “erythema,” “rash,” or “lump on head” should be avoided and more specific information should be provided, such as “erythematous macule on right leg,” “allergic dermatitis,” and “scalp cyst.”

b. Adverse Events Occurring Secondary to Other Events

In general, AEs occurring secondary to other events (eg, cascade events or clinical sequelae) should also be entered as separate AEs. For example, if severe diarrhea is known to have resulted in dehydration, both diarrhea and dehydration should be entered as AEs on the CRF, and if also serious, on the SAE form.

c. Persistent or Recurrent Adverse Events

A persistent AE is one that extends continuously, without resolution between subject evaluation time points. Such events should only be recorded once in the CRF unless their severity increases. If a persistent AE becomes more severe or occurs more frequently, it should be recorded again on the AE CRF with the increased severity grading.

A recurrent AE is one that occurs and resolves between subject evaluation time points and subsequently recurs. All recurrent AEs should be recorded individually on the AE CRF.

d. Abnormal Laboratory Values

Only clinically significant laboratory abnormalities that require active management will be recorded as AEs on the CRF and SAE form (if applicable). For example, abnormalities that require study drug dose modification, discontinuation of study treatment, more frequent follow-up assessments, further diagnostic investigation, etc.

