## 2.2. Definition of Dose-Limiting Toxicity (DLT)

A Dose-limiting Toxicity (DLT) is defined as follows:

- Allergic reaction requiring medical intervention
- Acute bronchospasm requiring medical intervention
- Other acute AEs of interest requiring immediate medical intervention

Allergic reactions and acute bronchospasm not requiring intervention (Grade 1) are usually considered subject-specific and are not included in the definition of DLT. In this protocol, allergic reactions and acute bronchospasm not requiring medical intervention are not included in the DLT definition since such reactions may not be product and dose-specific with QR-010.

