#### 4.10.1.3. DLT definition

Potential DLTs are reviewed and adjudicated by the DSMC. Adjudicated DLTs will be loaded from an excel file and summarized by treatment group. Individual subject listings will be provided for each DLT including severity.

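### The SAP's AESI9 (allergic reaction) term list matches neither angioedema nor throat constriction, both of which the protocol names as forms of allergic reaction, so such events would be left out of the AESI9 summary and listing

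*SAP*

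**What the plan says.** The only place where the documents list forms of allergic reaction is protocol 5.5.1: "Allergic reactions may include local dermatitis, angioedema, throat constriction, or anaphylaxis".

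SAP 4.10.1.2.9 sets the analysis rule: "Allergic Reaction is defined as the AEs of at least Grade 2 with the preferred term that contains" one of seven strings, "Hypersensitivity' or 'Alveolitis' or 'vasculitis' or 'urticaria' or 'dermatitis allergic' or 'anaphylactic' or 'anaphylaxis". The AESI sections give no standardised query, no medical review step and no use of the etiology field for AESI9.

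SAP 4.10.1.2 then calls for an overall summary of AESIs and DLTs together, tables of AESIs by SOC and PT, and AESI listings. In SAP 2.2 the first DLT criterion is "Allergic reaction requiring medical intervention". DLTs follow a separate route (SAP 4.10.1.3): the DSMC adjudicates them, and "Adjudicated DLTs will be loaded from an excel file and summarized by treatment group".

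**The concern.** AESI9 is the only prespecified grouping of allergic events in the SAP, and this is a first-in-human study of an inhaled oligonucleotide. A reader of the report will expect a row labelled allergic reaction to cover at least the forms that the protocol names. It does not, although the list includes vasculitis and alveolitis, which protocol 5.5.1 does not mention.

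The protocol's recording convention makes the gap practical. Section 12.4.3 says: "Signs and symptoms should be recorded on the AE CRF rather than the unifying diagnosis", and sends the diagnosis to the etiology field. An allergic episode seen as throat constriction would therefore tend to be entered as that sign, while AESI9 reads only the preferred term. For angioedema the convention makes no difference, because an event coded as angioedema fails to match in any case.

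The visible risk is an inconsistent report. A treated angioedema could be adjudicated as an allergic DLT and yet be missing from AESI9 in the same overall summary.

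**Working it through.** There is no planned figure to reproduce. The check has two parts.

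**1. String match.** The inputs are the four forms in protocol 5.5.1 with plausible coded variants, and the strings of every AESI that is defined by preferred term (AESI1, 2, 3, 5, 6, 7 and 9). The rule is a case-insensitive 'contains'.

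| Term tested | AESI9 | Any other term-based AESI |
|---|---|---|
| anaphylaxis; anaphylactic reaction | match | none |
| dermatitis allergic | match | none |
| local dermatitis; dermatitis; dermatitis contact | no match | none |
| angioedema | no match | none |
| throat constriction; throat tightness | no match | none |

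The lists nearest to an airway reaction are bronchospasm, "Bronchospasm' or 'asthma' or 'wheezing' or 'bronchial obstruction", and dyspnoea, "dyspnoea' or 'orthopnoea". Neither catches the missing forms. AESI4 (liver tests) and AESI8 (oximetry) are defined from measurements and do not group allergic events.

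Of the four named forms, anaphylaxis is found, dermatitis is found under one coding only, and angioedema and throat constriction are not found. The documents do not give the preferred term for throat constriction. 'Throat tightness' is an assumption, as is 'dermatitis contact'.

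**2. Effect of one missed subject.** The planned cohort is 6 QR-010 and 2 placebo (SAP 4.1), with four cohorts in each part and placebo pooled within a part (SAP Tables 3 and 4). One subject is 1/n of a column:

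- QR-010 dose group: 1/6 = 16.7 percentage points
- Pooled placebo in one part: 1/(4 × 2) = 1/8 = 12.5 points
- All active subjects in one part: 1/(4 × 6) = 1/24 = 4.2 points

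These figures assume no cohort expansion.

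The documents give no event rate. As an assumption only, let a proportion p of subjects have a Grade 2 or higher event of these kinds and no other matching term. The chance of at least one such subject is 1 − (1 − p)^n:

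| p (assumed) | n = 6 | n = 24 |
|---|---|---|
| 2% | 0.114 | 0.384 |
| 5% | 0.265 | 0.708 |
| 10% | 0.469 | 0.920 |

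So the gap may never matter in a given dose group. It could well matter once in a whole part if such events are not rare.

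**The case against.** The strongest reply is that little depends on AESI9, and most of that reply stands.

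- **DLTs and the MTD.** Because allergic reaction is a DLT criterion, a reader might infer that the gap distorts dose escalation. The documents do not support this. DLTs are adjudicated by the DSMC from unblinded cohort safety data and loaded from a separate file. Protocol Table 2 has no allergic-reaction entry, so the expedited DSMC review of AEs of interest as defined in the protocol (SAP 2.5.2) does not use this list either.
- **Visibility elsewhere.** SAP 4.10.1.1 reports all TEAEs by SOC and PT and lists those of Grade 2 or higher. Since AESI9 takes only Grade 2 or higher events, every treatment-emergent event that it misses is in that listing. It is just not grouped as allergic.
- **Direction of bias.** A reader might infer that allergic incidence is biased low overall. That is not shown. The list takes any alveolitis or vasculitis without asking for an allergic cause, so it may also over-count, and the net direction is unknown.
- **Status of the comparator.** Protocol 5.5.1 gives examples in a section on withdrawal; it is not an analysis definition. AESI9 is an SAP addition, so no protocol AESI definition is contradicted. Even so, 5.5.1 is the documents' only account of what an allergic reaction looks like, and a grouping with that name should cover it.
- **Dermatitis.** Protocol 12.4.3 steers sites away from vague terms and offers allergic dermatitis as a model entry. Dermatitis judged allergic may therefore reach the matching code, so this part of the gap is partial. Adding every dermatitis term would bring non-allergic skin events into the table.

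The omission of angioedema and throat constriction remains. Neither the other AESI lists nor any stated review step catches them.

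**Conclusion.** The point holds as a gap in one search list. AESI9 as written does not find angioedema or throat constriction, and finds local dermatitis only under one coding. An omission needs three things: such an event occurs, it is Grade 2 or higher, and the subject has no other term that matches. A subject whose episode also codes to a hypersensitivity or anaphylaxis term is still counted. When all three hold, the AESI9 summary and listing lose that subject, which is about 17 percentage points in a planned QR-010 dose group.

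The conclusion for angioedema assumes only that the coded term contains that word and none of the seven strings. For throat constriction it also assumes a preferred term such as 'throat tightness'. A certain undercount, a downward bias in overall allergic incidence, or an effect on DLTs or the MTD would each go further than the documents allow. The correction is worth making because it is cheap and prevents an AESI row from disagreeing with the DLT row beside it.

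**What to change.** Before database lock, amend SAP 4.10.1.2.9 as follows.

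1. Add preferred terms containing 'angioedema'.
2. Add the coded equivalent of throat constriction, for example 'throat tightness'. Confirm it in the MedDRA version used for coding: SAP 4.10.1.2 bases the AESI definitions on version 17.1, while SAP 4.2.9 codes events with the latest version at SAD lock.
3. Do not add every dermatitis term. Include a dermatitis term other than 'dermatitis allergic' only when a medical review blinded to treatment, or the etiology recorded on the CRF, indicates an allergic cause. Sponsor personnel may be unblinded (protocol 4.2, SAP 2.5.2), so the reviewer must be someone without access to treatment assignment.

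Fixing the list before lock, and documenting it, also prevents later additions from looking data-driven.

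The cost is one SAP sentence, an edit to the search code and a short term review. The downside is small: an occasional non-allergic throat event may be included, and it would be visible in the AESI listing.

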#### 4.10.1.3. DLT definition

Potential DLTs are reviewed and adjudicated by the DSMC. Adjudicated DLTs will be loaded from an excel file and summarized by treatment group. Individual subject listings will be provided for each DLT including severity.

#### 4.10.1.4. Change FEV1 ≤ -15% from baseline

The number of subjects with a change from baseline of FEV1 (L) ≤ -15% at least once and overtime will be summarized by treatment group. FEV1 evolution will be graphically presented for those subjects. A listing will be provided.

### 4.10.2. Laboratory Data

Local laboratory measurements are performed for this study, thus different units and normal ranges may be collected. Summary statistics will be provided when relevant.

#### 4.10.2.1. General Display

Laboratory measurements obtained will be summarized by treatment group overtime following analysis time points (time windows) that may differ according to parameter data collection.

Descriptive statistics for the continuous data of actual results and change from baseline for each time point will be presented. Frequencies and percentages per time point will be presented for categorical data.

Frequencies and percentages of subjects with values outside of the normal ranges overall (post-baseline) and for each time point will be presented.

Shift tables summarizing the count of subjects below, within and above the normal ranges at baseline and to maximum and to minimum value during treatment and after treatment for MAD and after treatment only for SAD will be presented. For shift tables all post-baseline assessments will be used (in particular unscheduled assessments).

Listing of laboratory data will be presented. A listing presenting the data for clinically relevant abnormal values will be provided.

#### 4.10.2.2. Hematology

Hematology includes: hematocrit, hemoglobin, erythrocyte mean corpuscular HGB concentration, erythrocyte mean corpuscular hemoglobin, erythrocyte mean corpuscular volume, erythrocytes, white blood count, segmented neutrophils, bands, total neutrophils, lymphocytes, monocytes, eosinophils, basophils, platelet count).

All analyses described in the general display section will be performed when possible.

#### 4.10.2.3. Chemistry

Serum chemistries will include sodium, potassium, chloride, bicarbonate, blood urea nitrogen (BUN), creatinine, glucose, calcium, phosphorus, SGPT/ALT, SGOT/AST, GGT, alkaline phosphatase, bilirubin (total and direct), uric acid, lactic dehydrogenase (LDH), albumin, total protein, triglycerides, and cholesterol. Creatinine clearance is to be calculated using the Cockcroft-Gault equation adjusted for actual body weight.

All analyses described in the general display section will be performed when possible.

#### 4.10.2.4. Coagulation tests and Direct Antiglobulin Test

Coagulation tests include INR, PT, APTT, fibrinogen and total complement (CH50). All analyses described in the general display section will be performed when possible.

Direct Antiglobulin test results will be summarized over time and reported in listing. They will be included in Coagulation outputs.

#### 4.10.2.5. Urinalysis

Urinalysis (by visual inspection and dipstick) will include color and appearance, microalbumin, casts, crystals, epithelial cells, erythrocytes, specific gravity, pH, protein, glucose, occult blood, ketones, bilirubin, leukocytes, leukocyte esterase, nitrite, and urobilinogen.

Urinalysis data will be reported in listings only.

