| Safety and Tolerability: | Safety will be assessed by monitoring AEs, vital signs, laboratory data (chemistries, hematology and urinalysis), immunogenicity evaluation, ECGs, pulmonary function, and physical examinations. 
 • Adverse events (AEs) • Physical examination (PE) at screening, baseline and end of study • Vital signs • Electrocardiograms (ECGs) at screening, baseline and end of study • Continuous cardiac monitoring (telemetry) • Spirometry (FEV₁) at baseline, 10, 30, and 60 minutes, and 2, 4, and 8 hours post-dose following the first dose to evaluate for provoked bronchospasm • Chest radiograph at screening and end of treatment (MAD only) • Laboratory analysis for signs of toxicity: hepatic, renal, immunogenicity |
| PK: | Subjects will provide blood, urine and expectorated sputum samples for presence of QR-010 at multiple time points. |
| Exploratory Safety and Efficacy: | The following will be performed or collected for exploratory evaluation and analysis: 
 • Blood (serum and plasma) and expectorated sputum for inflammatory biomarkers • Spirometry (FEV₁) baseline, weekly during dosing, end of study, and at the follow-up visits (MAD Cohorts only) • Cystic Fibrosis Questionnaire-Revised Respiratory Symptom Score (CFQ-R RSS) at baseline, prior to dose 7, and end of treatment (MAD Cohorts only) • Sweat chloride determination by pilocarpine iontophoresis at screening (all cohorts), on the last dosing day, and at follow-up visits 7 and 8 days after last dose (MAD cohorts only) |

| | |

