3.2 Secondary Objective(s)

The secondary objectives of the study are:

- To evaluate the change from baseline analysis for laboratory and vital signs
- To evaluate the pharmacokinetics (PK) of QR-010 administered by inhalation.

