4.1.2 Secondary Endpoint(s)

Safety: Changes from baseline to end of treatment or presence of abnormalities on frequent monitoring in laboratory parameters (chemistry, hematology, sputum microbiology, and urinalysis), vital signs, ECG, spirometry, and physical examinations. A chest radiograph will be obtained at screening and at end of treatment (MAD cohorts).

Pharmacokinetics: The PK of QR-010 will be examined in all stages of the study, from first dose through end of study. Specifically, subjects will provide blood, urine and expectorated sputum samples for PK assessments.

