8.5 Laboratory Evaluations

Laboratory evaluations will be performed according to the study schedule. For screening purposes, should the screening period require longer than 14 days (eg, CFTR genotype testing required longer than 14 days), safety evaluations (serum chemistries, hematologies, urinalysis, physical exam, vital signs, spirometry) must be re-obtained for confirmation of eligibility and enrollment into the study.

Serum chemistries will include sodium, potassium, chloride, bicarbonate, blood urea nitrogen (BUN), creatinine, glucose, calcium, phosphorus, SGPT/ALT, SGOT/AST, GGT, alkaline phosphatase, bilirubin (total and direct), uric acid, lactic dehydrogenase (LDH), albumin,

total protein, triglycerides, and cholesterol. Creatinine clearance is to be calculated using the Cockcroft-Gault equation adjusted for actual body weight. At screening, tocopherol (Vitamin E) levels will also be measured.

Hematologies will include a complete blood count: Complete blood count (CBC) with absolute differential (hematocrit, hemoglobin, white blood count, segmented neutrophils, bands, lymphocytes, monocytes, eosinophils, basophils, platelet count).

A Direct Antiglobulin Test (DAT) will also be performed at screening and 7 days after last dose.

Erythrocyte sedimentation rate (ESR) and C-reactive protein (CRP) will be measured at baseline, 24 hours post dose, and End of Study Visit for SAD cohorts, and at baseline, prior to doses 4, 7 and 10, and at the End of Treatment Visit for MAD cohorts. Two baseline measurements will be made; one on Day -1, and the other prior to dosing on Day 1.

Urinalysis (by visual inspection and dipstick) will include color and appearance, specific gravity, pH, protein, glucose, occult blood, ketones, bilirubin, leukocyte esterase, nitrite, and urobilinogen. In addition, microscopic analyses will be performed on samples with abnormal dipstick results. Urine microalbumin will be measured at baseline for SAD and MAD cohorts; end of study for SAD cohorts; and prior to dose 10 and end of study for MAD cohorts. Time of void will be recorded for each urine sample collected. At screening, testing for drugs of abuse will also be performed, specifically for amphetamines, methamphetamines, methylenedioxyamphetamine, cocaine, cannabinoids, phencyclidine, opiates, methadone, barbiturates, benzodiazepines, ethyl alcohol. Urine or blood testing for drugs of abuse is permitted.

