13.7.5 Other Safety Assessments

Other safety assessments, such as urinalysis, ECGs, and physical examinations will be summarized and listed as specified in the statistical analysis plan (SAP).

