## **5. CHANGES TO PLANNED ANALYSES**

As of this date, there have been no changes between the protocol-defined statistical analyses and pharmacokinetics analyses those presented in this statistical plan.

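### Urinalysis, including microalbumin, is part of a secondary safety endpoint but the SAP confines it to listings, so no urine-based renal marker is summarised by dose

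*SAP*

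**What the plan says.** Protocol 3.2 sets a secondary objective: "To evaluate the change from baseline analysis for laboratory and vital signs". Protocol 4.1.2 turns this into the secondary safety endpoint, which begins "Changes from baseline to end of treatment or presence of abnormalities on frequent monitoring in laboratory parameters (chemistry, hematology, sputum microbiology, and urinalysis". The synopsis describes the laboratory work as "Laboratory analysis for signs of toxicity: hepatic, renal, immunogenicity". Protocol 8.5 deals with microalbumin in the urinalysis paragraph: "Urine microalbumin will be measured at baseline for SAD and MAD cohorts", then at end of study in SAD, and before dose 10 and at end of study in MAD.

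On analysis, Protocol 13.7.5 states: "Other safety assessments, such as urinalysis, ECGs, and physical examinations will be summarized and listed", and leaves the detail to the SAP. SAP Tables 10 and 11 define analysis windows for urinalysis. SAP 4.10.2.5 names the parameters, microalbumin among them, and ends: "Urinalysis data will be reported in listings only". SAP 5 says that "there have been no changes between the protocol-defined statistical analyses" and those in the SAP. The later post hoc SAP covers only ppFEV1, CFQ-R RSS, weight and sweat chloride.

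**The concern.** A by-subject listing meets neither half of the endpoint. It gives no change from baseline and no frequency of abnormalities, and it does not set dose groups beside placebo. This is the first clinical use of the product, and the protocol expects systemic absorption. The urine tests were scheduled in addition to serum chemistry. A modest dose-related rise in microalbumin, or a cluster of new proteinuria or haematuria that needed no treatment, would have to be picked out by eye from several hundred records. The reader of the clinical study report would not be told that a promised summary had been dropped.

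**Working it through.** The plan gives no figure on this point and the sample size has no power basis. The check is therefore a comparison of text, with two counts.

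**1. SAP output for each component of the Protocol 4.1.2 safety endpoint**

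| Component | SAP section | Output |
|---|---|---|
| Hematology, chemistry | 4.10.2.1 to 4.10.2.3 | Values, change, out-of-range counts and shifts by group |
| Sputum microbiology | 4.10.2.6 | Counts and frequencies |
| Vital signs | 4.10.3 | Values and change |
| ECG | 4.10.5 | Counts and percentages |
| Spirometry | 4.8, 4.10.1.4 | Values, change, counts of FEV1 falls |
| Urinalysis | 4.10.2.5 | Listing only |
| Physical examination | 4.10.4 | Listing of abnormal findings |
| MAD chest radiograph | none | none |

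SAP 4.10.2.1 is a general rule that would give urinalysis a by-group display. Section 4.10.2.5 replaces it with listings, so the windows in Tables 10 and 11 feed no summary.

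**2. Renal coverage elsewhere.** SAP 4.10.2.3 applies the full general display to BUN, creatinine and Cockcroft-Gault creatinine clearance. Serum renal markers are therefore compared descriptively by treatment group. Only the urine markers are not.

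**3. Volume (Protocol 7.4 and Appendix 2).** MAD urinalyses per subject after the first dose:
- Day 1 pooled (0 to 4 h, 4 to 12 h): 2
- Dose 2 (60 min, 4 h): 2
- Day 4: 1
- Doses 4, 7 and 10 (pre-dose, 60 min, 2 h): 3 × 3 = 9
- Days 33 and 54: 2

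Total 2 + 2 + 1 + 9 + 2 = 16, and 16 × 32 = 512. Three of the 16 are pre-dose samples, so all are post-baseline but not all are post-dose samples for their visit. Microalbumin has 2 post-baseline values per MAD subject and 1 per SAD subject: 2 × 32 + 1 × 32 = 96. None is tabulated.

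**4. Windows.** Table 11 has 2 (Day 3) + 1 (Day 4) + 9 (Days 8, 15, 22) + 2 (Days 33, 54) = 14 post-baseline time points. The difference, 16 − 14 = 2, is the two Day 1 pooled samples. The first interval in Table 11 runs from the end of the Day 1 dose to 180 minutes after the Day 3 dose, so both pooled samples fall into the Day 3 60-minute slot. In Table 10 the Day 2 interval likewise opens at the Day 1 dose and takes in the SAD pooled samples. SAP 4.2.7 gives no rule for several urinalysis values in one interval.

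**5. Microalbumin schedule.** Protocol 8.5 and Table A.2-5 place the on-treatment sample before dose 10 (Day 22). SAP Table A.2-3 marks it on Day 10 (dose 5), yet the text of that table says dose 10. SAP Table A.2-5, which covers dose 10, omits it.

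**The case against.** A reader might infer that no renal signal at all is compared by dose. The documents do not support that. The serum markers get values, change from baseline, out-of-range counts and shift tables by group. Laboratory abnormalities that need active management also become adverse events (Protocol 12.4.3), and these are tabulated by treatment group.

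A reader might also infer that the SAP dropped a specified change-from-baseline table. It did not. The endpoint offers two alternatives, change or presence of abnormalities. The by-dose change and shift summaries in Protocol 13.7.4 are limited to hematology and chemistry, and 13.7.5 leaves the form of the urinalysis summary to the SAP. That objection stands as far as it goes. But 13.7.5 hands over how to summarise, not whether to.

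Three further objections have some weight:
- **Local laboratories.** Units and ranges differ between sites, and neither document gives an assay or unit for microalbumin. Pooled means may not be possible. This limits the form of the summary, but counts above the local range, or dipstick categories, could still be tabulated.
- **Other oversight.** The DSMC reviews unblinded safety data after each cohort, and the sponsor may be unblinded. That protects subjects during the trial but does not put a summary in the report.
- **Small groups.** With 6 active and 2 placebo subjects per cohort, any table is descriptive. That is true of every safety table in this study.

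**Conclusion.** The point holds for urine markers. Part of a secondary safety endpoint has no by-dose summary, contrary to Protocol 13.7.5, and SAP 5 does not disclose it. What is missing is a summary; no explicitly specified table was removed, and renal safety as a whole is not left unexamined. In size, about 512 scheduled MAD urinalyses and up to 96 post-baseline microalbumin values across both parts would be reported only line by line. These counts assume 32 subjects in each part, full attendance and no cohort expansion. The primary endpoints (adverse events and DLTs) are unaffected.

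The text comparison is certain. Whether microalbumin can be pooled as a continuous measure is not, because it depends on local assays that the documents do not describe. The chest radiograph and schedule points are real but secondary: Protocol 4.1.2 says only that the film will be obtained, and no analysis of it is specified.

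**What to change.** Replace the last sentence of SAP 4.10.2.5 with descriptive summaries by dose group and placebo, keeping the listings:

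- **Microalbumin:** value and change from baseline at SAD Day 8, and at MAD Day 22 pre-dose and Day 54, where local assay and units permit; otherwise the number of subjects above the local normal range.
- **Dipstick protein, occult blood and glucose:** baseline-to-worst shift tables, or frequencies of abnormal results.
- **Windows:** use Tables 10 and 11, but give the Day 1 pooled samples their own interval and state a rule for several values in one interval.
- **Microalbumin schedule:** reconcile SAP Tables A.2-3 and A.2-5 with Protocol 8.5 and Protocol Table A.2-5.
- **Chest radiograph:** a by-dose count of findings at the MAD end-of-treatment visit.

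If listings only is intended, for urinalysis or for physical examinations (which are in the same position), record and justify it in SAP 5. If the SAP can no longer be amended, the tables can go in the study report, identified as unplanned, as Protocol 13.1 allows. The cost is a few extra descriptive tables from data already scheduled for collection, with no new procedures for subjects.
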